## 7. Risks

a. Medical risks, listing all procedures, their major and minor risks and expected frequency.

This research adds no additional risk to a patient undergoing a DP. Patients will be randomized to one of two widely accepted drainage techniques. If in the opinion of the surgeon at the time of surgery, one technique has a perceived advantage over the other, that patient will undergo the technique felt to be indicated.

Therefore, medical risks are those of DP: bleeding, infection, anesthesia risks, fistula formation, pain, stroke, death, myocardial infarction, non-healing wound, diabetes mellitus, need for reoperation.

b. Steps taken to minimize the risks.

Preoperative anesthesia evaluation, cardiology clearance when necessary, optimization of the management of patient's comorbities, perioperative antibiotic prophylaxis, perioperative and postoperative pain control, nutritional support.

c. Plan for reporting unanticipated problems or study deviations.

The principal investigator will monitor patient safety and care. Adverse events or unanticipated problems will be reported in the Department of Surgery monthly research meeting. Necessary changes to the study protocol will be made on an as needed basis.

This is a Level I study under the SKCCC Data and Safety Monitoring Plan. The SKCCC Clinical Research Office Quality Assurance Group will perform periodic audits on this study. All trial monitoring and reporting will be reviewed annually by the SKCCC Safety Monitoring Committee.

d. Legal risks such as the risks that would be associated with breach of confidentiality.

Participants will be required to sign an informed consent in order to enroll in this study. The privacy and confidentiality of the patients in this study will be preserved in the standards of HIPAA and privacy policy of the Johns Hopkins Hospital. All de-identified protected health information will be saved in password-protected hospital computer drives. Access to data collected in this study will be limited to the research team members. If a patient's confidentiality is accidentally breeched, the patient will be notified by the principal investigator and measures will be taken to rectify such events.

e. Financial risks to the participants.

Monetary risks are similar to those for any patient undergoing DP. This includes the cost of surgery and rehabilitation, time off from employment, and adjuvant therapy if indicated.

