Despite evidence-based data questioning the utility of routine drainage in pancreatic surgery, most surgeons around the world and at Johns Hopkins still routinely drain the pancreatic transection margin following distal pancreatectomy with closed suction drains. However, some surgeons have abandoned closed suction drains for closed non-suctioning drains which function by draining to gravity pressure. These drains still prevent fluid collections and allow for early detection of complications but do not generate the same high negative pressures. Clearly the optimal drain to drain the peritoneal cavity following distal pancreatectomy is still unclear for the majority of pancreatic surgeons.

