## 4. Study Procedures

a. Study design, including the sequence and timing of study procedures (distinguish research procedures from those that are part of routine care).

Head-to-head Prospective Randomized Trial: At operation, consented patients will be randomized after removal of the DP specimen to either drain with a single closed suctioning Jackson Pratt versus a closed non-suctioning straight drain. Patients will be stratified based on the surgeon's assessment of the gland texture, as hard versus soft. All drains will be positioned near the pancreatic transection margin. Recorded variables at the time of surgery will include pancreatic gland texture, pancreatic duct diameter, blood loss, and intraoperative time.

Since both types of drains are currently used by surgeons at JHH, we believe that there is no significant change to what is considered routine care of these patients. Surgeon preference currently dictates the drain choice at the time of operation.

b. Study duration and number of study visits required of research participants.

Our plan is to randomize 134 pts per arm (268 total). Approximately 115 DPs are performed annually at JHH. Based on a patient recruitment rate of 90%, the estimated period to complete this trial will be 31 months.

The endpoints of the study are events noted in the 90-day postoperative period, therefore no additional study visits will be required for the study participants, other that their postoperative hospital stay and routine postoperative visits. A case report form (Appendices Section) will be used to facilitate routine collection of standardized information from every subject in order to reliably detect and grade POPF and other complications. This form will be completed by the study coordinator on the day of discharge +/- one day, on the day of re-discharge (in case of readmission) +/- one day, on the day of any postoperative outpatient visit +/- one day, and at 90 days from surgery +/- two weeks. This information will be collected either over the telephone.or in person (eg, in the hospital inpatient setting or at ordinary, outpatient, patient-care clinic visits).

c. Blinding, including justification for blinding or not blinding the trial, if applicable.

This will not be a blinded trial.

d. Justification of why participants will not receive routine care or will have current therapy stopped.

Participants in both groups will receive standard surgical and post-surgical care.

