## **Study Statistics**

a. Primary outcome variable.

The primary endpoints of the study will be the development of POPF, as recently defined and graded by the International Study Group of Pancreatic Surgery.

b. Secondary outcome variables.

Secondary endpoints will include length of hospital stay, need for enteral or parenteral nutrition, need for radiologic or surgical intervention, septic complications, and perioperative mortality.

c. Statistical plan including sample size justification and interim data analysis.

The incidence of either POPF after DP is approximately 30%, based on retrospective studies validating the ISGPS definition. A clinically significant reduction of the event rate to 15% in the treatment group would require enrollment of 134 patients per arm (268 total), assuming a 2-tailed test with  $\alpha$  of 0.05 and power of 0.80. We therefore plan to consent and enroll 300, accrue 270 (roughly 90% of 300).

Interim analysis will be performed after recruitment and analysis of 150 patients.

d. Early stopping rules.

The trial will be terminated prematurely, if statistically significant differences between the groups or potential safety risks are identified.

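### The surgeon may choose the drain on his or her own judgement during surgery, but the plan does not say whether this comes before or after allocation, and it names no analysis population

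*Combined protocol and SAP*

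**What the plan says.** Section 4a (Study Procedures) states that "consented patients will be randomized after removal of the DP specimen to either drain", with stratification by the surgeon's "assessment of the gland texture, as hard versus soft". Section 4c adds "This will not be a blinded trial".

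Section 7a (Risks) first says that patients will be randomised to one of two accepted techniques. It then says that if, in the surgeon's opinion during the operation, "one technique has a perceived advantage over the other, that patient will undergo the technique felt to be indicated".

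On current practice, section 4a reports that "Surgeon preference currently dictates the drain choice at the time of operation". The Background section says that "most surgeons around the world and at Johns Hopkins still routinely drain the pancreatic transection margin following distal pancreatectomy with closed suction drains", and that some surgeons have given these drains up for non-suctioning ones.

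Study Statistics gives the endpoints, the sample size, one interim look and a stopping rule. The difference of 30% versus 15% "would require enrollment of 134 patients per arm (268 total), assuming a 2-tailed test" at α 0.05 and power 0.80, with 300 to be consented and 270 accrued. No analysis population is named there or elsewhere. The removal criteria in section 4f do not mention overrides, and section 5 has no exclusion for surgeon preference.

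**The concern.** Allocation takes place during the operation, so a judgement made during the operation can fall on either side of it. The two readings describe different trials.

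- **Before allocation.** The patient is not randomised. Validity and effect size are untouched. The costs are slower accrual and a population limited to patients for whom the surgeon accepts either drain.
- **After allocation.** A randomised patient receives the other arm's drain. Analysis by assigned arm remains valid, but the observed difference is diluted and power falls.

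The missing analysis population makes the second reading worse. The plan does not propose to analyse by drain received, but it does not rule that out, nor does it rule out dropping overridden patients. Either could bring selection bias, because the surgeon's reason for overriding may be related to fistula risk, for example through gland texture. In an unblinded trial, how these patients are counted should be fixed before outcomes are known.

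**Working it through.** **Inputs from the documents.** Event rates of 30% and 15%, two-sided α 0.05, power 0.80, 134 per arm, 300 consented and 270 accrued (Study Statistics, c); 115 operations a year, 90% recruitment and 31 months (section 4b). The override rate *c* is not given, so 2%, 5% and 10% are assumptions.

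**The plan's sample size.** The pooled-variance normal approximation is

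n = [1.96·√(2·p̄(1−p̄)) + 0.8416·√(p₁(1−p₁)+p₂(1−p₂))]² / (p₁−p₂)²

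With p̄ = 0.225 this is (1.1575 + 0.4889)² / 0.15² = 120.5, or 121 per arm. The continuity correction, (n/4)·[1 + √(1 + 4/(n·0.15))]², gives 133.5, or 134 per arm. The plan's figure is therefore reproduced exactly by the corrected formula. Power at 134 per arm is 0.802 corrected and 0.840 uncorrected.

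**Overrides after allocation, analysed as assigned.** Each overridden patient is given the average event rate of the drain received:

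- suction arm: 0.30(1−c) + 0.15c = 0.30 − 0.15c
- non-suction arm: 0.15(1−c) + 0.30c = 0.15 + 0.15c

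At c = 5% these are 29.25% and 15.75%; at c = 10% they are 28.5% and 16.5%. With overrides in both arms the 15-point difference becomes 13.5 and 12 points. Power at 134 per arm, corrected (uncorrected in brackets):

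| Where overrides occur | 5% | 10% |
|---|---|---|
| Non-suction arm only | 0.752 (0.796) | 0.698 (0.747) |
| Suction arm only | 0.762 (0.806) | 0.718 (0.767) |
| Both arms | 0.708 (0.757) | 0.598 (0.654) |

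At 2% in both arms, power is 0.766 (0.809). Uncorrected power stays at 0.80 up to about c = 4.6% in the non-suction arm alone, or 2.6% in both arms. Corrected power starts at 0.802, so there is almost no slack.

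**Judgement before allocation.** A share *e* of patients is not randomised. The effect depends on what the reduction from 300 to 270 is meant to cover.

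- *The margin absorbs these patients:* 300(1−e) = 285 at 5% and 270 at 10%, both at least 268. The limit is 1 − 268/300 = 10.7%.
- *The margin is fully used by other losses (worst case):* 270(1−e) = 256.5 at 5% and 243 at 10%, with power 0.782 (0.824) and 0.757 (0.803). To keep 268 randomised, 268/(0.90(1−e)) = 314 or 331 must be consented. Accrual takes 12·268/(115·0.90·(1−e)) = 32.7 or 34.5 months. At e = 0 this formula gives 31.1 months, which matches section 4b.

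**The case against.** The strongest reply is that the benign reading is the natural one. Randomisation waits until the specimen is out and is stratified by the surgeon's assessment of the gland, so the surgeon has judged the gland before any drain is assigned. The sentence in section 7a sits under medical risks, where it reads as a safeguard rather than a crossover rule. On that reading no dilution occurs. This is plausible, but it is not written, and the sentence follows directly on the statement that patients will be randomised.

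Second, nothing in the documents gives an override rate. The statements on preference describe habit outside the trial, not how often a surgeon would replace an allocated drain. That is right. The power figures are conditional, and the lowest one needs 10% override in both arms. The preferences do show that the question is a real one at this site.

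Third, the model gives overridden patients the average risk of the other arm. If overrides pick out patients at unusual risk, the true loss could be smaller or larger. This also stands.

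Fourth, section 4b says "Based on a patient recruitment rate of 90%, the estimated period to complete this trial will be 31 months". The same 90% links 300 to 270, so the margin may already cover consented patients who are never randomised. If so, the worst-case accrual figures count the same loss twice, which is why they are only an upper bound. The margin does not help with overrides after allocation, because 270 is only two above 268.

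Finally, assigned-arm analysis is the usual default, and silence is not evidence of another plan. True, but the plan expressly allows departures from allocation and should say how they are counted.

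**Conclusion.** The concern holds and should be fixed; confidence is medium. Followed literally, sections 4a and 7a allow an allocated drain to be replaced, and no part of the plan sets the order of events or says how such patients are analysed.

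If the judgement comes after allocation, the cost is lost power, not a false-positive risk, provided the analysis is by assigned arm. That loss is slight at 2% override and material at 5 to 10%, especially if it affects both arms. If the judgement comes before allocation, the comparison is sound and accrual is the only exposure. The size rests on assumed override rates, on average risk among overridden patients, and on the plan's own 30% and 15%.

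**What to change.** Reconcile sections 4a and 7a, and carry the result into section 5 and Study Statistics:

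1. After specimen removal and before the allocation is opened, the surgeon records, together with gland texture, whether either drain is acceptable. If not, the patient is not randomised, is treated at the surgeon's discretion and is logged.
2. State in Study Statistics that the primary analysis includes every randomised patient in the assigned arm, whatever drain was placed.
3. Record any later override and report it by arm, with the reason.

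The surgeon's freedom of choice is unchanged, and no change to the sample size is asked for.

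The cost is a few sentences and one recorded item. The case report form is in an appendix that was not available and may already capture the drain placed. Accrual may slow: not at all up to about 10% exclusion if the 30-patient margin covers it, and at most to about 32.7 or 34.5 months at 5% or 10% exclusion if it does not. Results would apply to patients for whom the surgeon accepts either drain.

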## 8. Benefits

a. Description of the probable benefits for the participant and for society.

This study aims to assess whether one drainage technique is associated with decreased postoperative morbidity. If one technique is found to be superior to the other, both the individual study participants as well as the entire society will benefit, by minimizing the somatic, psychological, and financial costs associated with DP complications. All participants will receive the superb surgical and medical care provided by the Johns Hopkins Hospital.

Date: 12-08-2012 Principal Investigator: [name] Application Number: NA\_00080937

## 9. Payment and Remuneration

a. Detail compensation for participants including possible total compensation, proposed bonus, and any proposed reductions or penalties for not completing the protocol.

Patients will not be monetarily compensated for participating in this study.

#### 10. Costs

a. Detail costs of study procedure(s) or drug (s) or substance(s) to participants and identify who will pay for them.

The costs of this study are mainly administrative. These include salary support for the study coordinator and conference-related expenses for the investigators. No additional staff will be acquired for this project. We will attempt to obtain intramural funding to cover these expenses. The cost of perioperative care of patients undergoing DP at the Johns Hopkins Hospital are not expected to differ between the treatment and control groups. Some surgeons use suctioning drains and other use non-suctioning drains; therefore on average this trial is expected to result in no additional cost.
